## 6. Trial endpoints

Clinical endpoints will be analyzed in all subjects who are enrolled, regardless of whether the trial treatment administered successfully completed for the desired duration. A subject will be considered enrolled in the trial when he/she is randomized to one of the treatment arms of the study. All endpoints are subject-based unless otherwise specified.

The primary endpoint is subject-based of the longer of a 12-month or end of study treatment endpoint of the first occurrence of index limb arterial occlusion, surgical intervention,

endovascular intervention, amputation of the affected limb (primary patency and limb salvage), MI, ischemic stroke or death (survival)

The secondary endpoints are subject-based on the longer of a 12-month or end of study treatment endpoints that include: (a) the first occurrence of any individual component of the primary endpoint, (b) the first occurrence of the following during follow-up: cardiovascular death, or MI, or ischemic stroke, or any amputation above the ankle and (c) severe bleeding defined according to the Global Utilization of Streptokinase and Tissue plasminogen activator for Occluded coronary arteries (GUSTO) classification

The tertiary endpoint is based on the longer of a12-month or end of study treatment moderate bleeding according to the GUSTO classification

Clinically indicated DAPT duration will be based on the longest pre-discharge following index peripheral intervention procedure DAPT duration. This will be determined based on: peripheral intervention device IFUs, preceding coronary intervention, acute coronary syndrome or other guideline-based clinical or device specific DAPT duration.

Study treatment will be discontinued at the first occurrence of a primary endpoint as defined in the table below. Patients, however, can resume taking aspirin, Clopidogrel, or both based on their provider's clinical decision.

Primary endpoint definition(s)	Secondary/Tertiary endpoint definition(s)
Occlusion of the target limb documented by any imaging procedure performed clinically	As described in section 6, except for:
any maging procedure performed ennearly	GUSTO bleeding criteria:
Any surgical or endovascular	1. Severe or Life-threatening: Intracerebral hemorrhage resulting in substantial
revascularization procedure on the index limb	hemodynamic compromise requiring treatment
Amputation above the ankle of the index	2. Moderate: Requiring blood transfusion but not resulting in hemodynamic

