limb Death from any cause	compromise
Ischemic stroke: An episode of neurological dysfunction caused by focal cerebral, spinal, or retinal infarction confirmed by a neurologist	3. Mild: Bleeding that does not meet above criteria
MI: Detection of a rise in cardiac troponin	
(cTn) with at least one value 3x above the	
99th percentile upper reference limit (URL) and with at least 1 of the following:	
Symptoms of ischemia	
• New or presumed new significant ( $\geq 1$	
mm) ST- segment–T wave (ST–T)	
changes or new left bundle branch block (LBBB)	

• Development of pathological Q waves in the ECG	
--	--

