• Current participation in another drug or device trial that requires interruption of dual-antiplatelet therapy with aspirin or clopidogrel for the duration of the study	
• Planned surgeries, endovascular or other non-vascular or cardiac procedures	
• Concurrent warfarin or other chronic oral anticoagulant therapy	
• Contraindication(s) to the use of AT (history of intra-cerebral bleed, presence of intracerebral mass, recent or <6 weeks gastrointestinal bleed, blood transfusion within the last 6 weeks, any trauma requiring surgery or blood transfusion within the last 4 weeks or any surgical procedure within the last 4 weeks.	
Angiographic:	
• Endovascular intervention to iliac, FB or BTK artery bypass graft	
• Persistent, intraluminal thrombus of the proposed target lesion at the completion of the index procedure	
• Perforated vessel as evidenced by extravasation of contrast media	
• Vascular graft, aneurysm or postsurgical stenosis of the target vessel	

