## **23.Adverse Events**

All Adverse Events (AE) and Serious Adverse Events (SAE) will be reported through EDC and analyzed through study follow-up period.

Term	Definition
Adverse Event (AE)	Any untoward medical occurrence in a subject. This definition does not imply that there is a relationship between the adverse event and the treatment under investigation.
	Note 1: In addition, the definition of AE applies to any event with an onset post- randomization procedure or to any underlying diseases, present at baseline, that exacerbate in severity post- randomization procedure. Therefore, any underlying disease that was present at the time of enrollment is not to be reported as an AE, but any increase in the severity in the underlying disease is to be reported as an AE. This definition includes events occurring in the follow-up period.
Serious Adverse Event (SAE)	
 
An adverse event that:
 
led to death;
 
led to a serious deterioration in the health of the subject that: 
 
resulted in a life-threatening illness or injury,
 
resulted in a permanent impairment of a body structure or a body function,
 
 
 

Clinical events to be considered and reported as expected SAE include, but are not limited to:

- MAE (see definitions)
- Stent Thrombosis
- Bleeding complication as per GUSTO definition
- Vascular event requiring target limb surgical or endovascular intervention or amputation
- Any hospitalization

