#### 24. Risk-benefit analysis

Based on review of the scientific literature, outcomes of design verification, the results of preclinical studies, and known adverse drug effects, the benefit of treatment with the aspirin and clopidogrel post-iliac, FP and BTK endovascular intervention outweighs the risks. However, the effect of unknown factors accounting for unanticipated side effects cannot be completely excluded, therefore observation and follow-up of subjects is required as outlined in the protocol.

Risks associated with aspirin and clopidogrel drug therapy may include:

- a. Allergic reaction
- b. Amputation
- c. Aneurysm
- d. Angina/coronary ischemia
- e. Arrhythmia
- f. Arteriovenous fistula
- g. Death

- h. Drug-drug interactions
- i. GI bleeding
- j. Hemorrhage/hematoma
- k. Hypotension/Hypertension
- l. Myocardial infarction (MI)
- m. Need for urgent intervention or surgery
- n. Pseudoaneurysm
- o. Renal insufficiency or failure
- p. Restenosis of stented artery
- q. Rupture of the retroperitoneum or other organ
- r. Stroke
- s. Thrombosis / Thrombus
- t. Tissue ischemia/necrosis
- u. Vasospasm
- v. Vessel injury, examples include perforation, dissection, intimal tear, rupture
- w. Vessel occlusion

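### As printed, severe bleeding needs intracerebral hemorrhage and hemodynamic compromise together, so some non-fatal major bleeds grade mild and enter no endpoint

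*Combined protocol and SAP*

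**What the plan says.** Section 6 makes severe bleeding a secondary endpoint and moderate bleeding the tertiary endpoint, both by reference to the GUSTO classification. The table in the same section then prints criteria under a GUSTO heading:

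- Severe: "Severe or Life-threatening: Intracerebral hemorrhage resulting in substantial", continued on the next line as "hemodynamic compromise requiring treatment".
- Moderate: "Moderate: Requiring blood transfusion but not resulting in hemodynamic", with the word for compromise on the following line.
- Mild: "Mild: Bleeding that does not meet above criteria".

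No endpoint uses the mild grade. The primary composite closes with "endovascular intervention, amputation of the affected limb (primary patency and limb salvage), MI, ischemic stroke or death (survival", and the secondary composite likewise limits stroke to ischemic stroke. A non-fatal intracerebral bleed is therefore not picked up as a stroke in either.

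Bleeds are also captured outside the endpoints. Section 23 lists "Bleeding complication as per GUSTO definition" and any hospitalization among reportable serious adverse events. The Clinical Events Committee (CEC) adjudicates bleeding events and any stroke, and the DSMB reviews all adverse events.

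**The concern.** Nothing in the severe definition makes its two conditions alternatives. Intracerebral hemorrhage is the only bleed named, and the words that follow add a further requirement to it. A gastrointestinal bleed with shock then fails severe because of its site and fails moderate because compromise is present. It drops into the residual grade.

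The test arm adds 12 months of clopidogrel on top of aspirin, and severe bleeding is the secondary endpoint aimed at the harm of that exposure. Section 24 lists gastrointestinal bleeding among the drug risks, yet as printed no gastrointestinal bleed can be graded severe. A nearly empty severe category could then be read as evidence of safety when it partly reflects how the grade is worded. The mild category, which nobody tabulates as an endpoint, would mix serious bleeds with trivial ones.

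**Working it through.** The plan states no bleeding rate and no figure for this endpoint, so there is no number to reproduce. The check is to apply the rule to every possible case.

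**Inputs** (Section 6 table): three yes/no features, namely intracerebral site, hemodynamic compromise and transfusion, giving 2 × 2 × 2 = 8 profiles.

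**Rule as printed:** severe if intracerebral *and* compromise; otherwise moderate if transfused *and* no compromise; otherwise mild.

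**Rule with alternatives:** severe if intracerebral *or* compromise; otherwise moderate if transfused; otherwise mild.

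| Intracerebral | Compromise | Transfusion | As printed | With *or* |
|---|---|---|---|---|
| yes | yes | yes | severe | severe |
| yes | yes | no | severe | severe |
| yes | no | yes | moderate | severe |
| yes | no | no | mild | severe |
| no | yes | yes | mild | severe |
| no | yes | no | mild | severe |
| no | no | yes | moderate | moderate |
| no | no | no | mild | mild |

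**Count.** Profiles with intracerebral bleeding or compromise: 8 − 2 = 6. As printed they split 2 severe + 1 moderate + 3 mild = 6. With *or*, all 6 are severe. Four profiles move up: three from mild and one from moderate.

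**Internal consistency.** Compare two transfused extracranial bleeds. Without compromise the bleed is moderate and counts in the tertiary endpoint. Add compromise, so that the patient is sicker, and it becomes mild and counts nowhere. Excluding compromise from moderate makes sense only if compromise belongs in a higher grade. The printed severe grade does not receive those bleeds unless they are intracerebral. This inversion follows from the document alone.

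**The case against.** **Text extraction.** The table was read from a PDF by a program and is damaged in places: one line in its left column is garbled and two rows have run together. A missing *or* is therefore possible. Against that, the words joining the hemorrhage to its consequence sit unbroken on one line, which is where an *or* would have to fall, and the sentence reads cleanly across the line break. The risk stands as a caveat and is settled by looking at the source PDF.

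**GUSTO is cited by name.** Adjudicators might grade from the published classification and ignore the table cell. That classification is not reproduced in the documents and the CEC charter is not among them, so I rely on neither. If the committee already treats the conditions as alternatives, the change only brings the protocol into line with practice. Until then, the protocol's only printed criteria give the inverted grading.

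**Safety oversight is intact.** This stands. A reader might infer that serious bleeds would go unseen, and the documents do not support that: the reporting, adjudication and DSMB routes all remain. Those routes do not correct the endpoint grade, however.

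**Other internal support is weak.** The exclusion for "history of intra-cerebral bleed, presence of intracerebral mass" in Section 10 carries no compromise condition, but it is an entry criterion, not a grading rule. Section 24 lists "Rupture of the retroperitoneum or other organ" without calling it a bleed. I rest the case on the definition of moderate, not on these.

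**Conclusion.** The printed severe grade is wrong as written and should be corrected. Three of the 6 profiles with intracerebral bleeding or compromise fall to mild, and a fourth, the transfused intracerebral bleed without compromise, reaches only moderate. The direction is fixed: literal grading can only lower the severe count relative to the corrected rule. How many events would be misgraded cannot be said, because the documents give no bleeding rates.

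Three broader readings are tempting and do not hold:

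- That every intracerebral bleed without compromise goes uncounted. A transfused one is moderate and enters the tertiary endpoint.
- That fatal bleeds are lost. Death from any cause is in the primary endpoint. A bleed that leads to another counted event, such as a qualifying MI, is also counted through that event.
- That the trial loses a planned level of power to detect harm. Section 20 treats secondary endpoints descriptively, and the plan makes no power claim for bleeding.

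The primary endpoint and sample size are unaffected. The conclusion assumes that the extracted wording matches the source PDF and that the table is applied as printed.

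**What to change.** Replace the three criteria in the Section 6 table with:

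1. Severe or life-threatening: (a) any intracerebral hemorrhage, or (b) bleeding at any site that causes substantial "hemodynamic compromise requiring treatment".
2. Moderate: bleeding that needs transfusion and does not meet 1.
3. Mild: bleeding that meets neither 1 nor 2.

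Use identical wording in the CEC charter and date the change. If bleeds have already been adjudicated, have the committee re-grade them without knowledge of treatment arm and before the data are analyzed. Check the source PDF first; if it already has the two conditions as alternatives, no change is needed.

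The cost is one table cell, a matching charter line and any re-grading. No new data, visits or patients are required. The drawback is that the definition of a secondary endpoint changes, possibly while the trial is running, which is why the dating and the blinded re-grading matter.

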## 7. Trial design

This is a prospective, multi-center, two-arm randomized clinical trial to evaluate whether clopidogrel 75 mg QD on a background of ASA 81 mg for U.S. sites (75-100 mg/d for international sites) for clinically indicated duration with a minimum of 30 days or an additional 12 months will lead to an increased rate of primary patency, limb salvage and survival, in patients receiving endovascular treatment of PAD.

Up to 404 subjects at approximately 18 centers in the United States are planned. Assuming 10% attrition at 12 months, enrollment of a minimum of 404 would yield at least 368 evaluable subjects for the longer of a12-month or end of study treatment endpoint. No center will be allowed to enroll more than 40% of the subjects.

A schematic of the trial design is provided in Figure 1.

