	agents (history of intra-cerebral bleed, presence of intracerebral
	mass, recent or <6 weeks gastrointestinal bleed, blood
	transfusion within the last 6 weeks, any trauma requiring surgery
	or blood transfusion within the last 4 weeks or any surgical
	procedure within the last 4 weeks.
	Angiographic:
	• Endovascular intervention to iliac, FB or BTK
	artery bypass graft
	Persistent, intraluminal thrombus of the
	proposed target lesion at the completion of
	the index procedure
	• Perforated vessel as evidenced by extravasation of contrast media
	
 
Vascular graft, aneurysm or postsurgical stenosis of the target vessel
 

Multiple Interventions	Multiple interventions during an index procedure will be allowed as
During Index Procedure	long as the procedure is deemed successful and uncomplicated by the
	primary operator and no additional procedures are planned
Statistical Methods	
Sample size parameters	• The occurrence of the primary endpoint is expected
Sampre Size parameters	to be approximately 49% at 12 months in the
	control group 
	
 
A 30% relative risk reduction in the incidence of primary
 

	endpoint would be clinically important
	
 
To detect a 30% relative reduction in the 1-year primary
 

	event rate from $49\%$ to $34.0\%^{17}$ with $80\%$ power at the two sided 05 significance level assuming a 12 month
	two-sided, .05 significance level, assuming a 12-month
	two-sided, .05 significance level, assuming a 12-month recruitment period and a 1 0 % dropout rate at 1 year, a total
	two-sided, .05 significance level, assuming a 12-month recruitment period and a 1 0 % dropout rate at 1 year, a total of 404 (368+36) patients will be randomized (202 in each
	two-sided, .05 significance level, assuming a 12-month recruitment period and a 1 0 % dropout rate at 1 year, a total of 404 (368+36) patients will be randomized (202 in each group) and followed-up for endpoints for 12 months or until
	two-sided, .05 significance level, assuming a 12-month recruitment period and a 1 0 % dropout rate at 1 year, a total of 404 (368+36) patients will be randomized (202 in each
Statistical analysis	two-sided, .05 significance level, assuming a 12-month recruitment period and a 1 0 % dropout rate at 1 year, a total of 404 (368+36) patients will be randomized (202 in each group) and followed-up for endpoints for 12 months or until end of study treatment, whichever is longer

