## 14. Sample size estimate

The occurrence of the primary endpoint is expected to be approximately 49% in the control group, derived on the basis of current literature review and preliminary data form XLPAD registry.

A 30% relative risk reduction in the incidence of primary endpoint would be clinically important. To detect a 30% relative reduction in the primary event rate from 49% to34%  with 80% power at the two-sided, 0.05 significance level, assuming a 12-month recruitment period and a 10% dropout rate at 1 year, a total of 404 patients will be randomized (202in each group) and followed-up for endpoints for longer of a 12-month or end of study treatment period.

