## **Primary Endpoint**

For the primary endpoint of 12-month composite of primary patency, limb salvage, MI, ischemic stroke and survival, with 95% confidence bounds will be calculated in the active arm and compared to control treatment duration. If this bound is less than that of control, then the primary endpoint will be considered met. All enrolled subjects are to be assessed for adverse events at follow-up visits. Assuming a maximum of 10% attrition due to non-compliance, loss to follow-up or death or non-compliance with follow-up, a minimum of 184 subjects in each arm are expected to be evaluable for the primary endpoint.

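### With 404 randomised and 10% attrition, about 364 subjects (about 182 per arm) are evaluable, not at least 368 (184 per arm), and death is wrongly counted as attrition; the 80% power is kept

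*Combined protocol and SAP*

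**What the plan says.** The combined protocol and SAP gives the evaluable sample in three places.

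- Section 7 (Trial design) begins "Assuming 10% attrition at 12 months" and concludes that "enrollment of a minimum of 404 would yield at least 368 evaluable subjects".
- Section 20, under Primary Endpoint, puts it per arm. It begins "Assuming a maximum of 10% attrition due to non-compliance, loss to follow-up or death" and concludes that "a minimum of 184 subjects in each arm are expected to be evaluable for the primary endpoint".
- The Synopsis, under sample size parameters, shows how the total was built: "404 (368+36) patients will be randomized (202 in each" group).

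Section 14 gives the same total, "a total of 404 patients will be randomized (202in each group"), for 80% power at a two-sided 0.05 level with 10% dropout at one year. It does not give the evaluable number. Section 11 says that withdrawn subjects are not replaced, because the sample size already allows for attrition.

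On death, Section 6 makes death from any cause a component of the primary endpoint. The follow-up schedule in the Synopsis counts subjects who have died as complete for that endpoint.

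**The concern.** Sections 7 and 20 state floors, and Section 20 ties its floor to a maximum attrition of 10%. A floor should hold at the plan's own worst case, and this one fails there. Because withdrawn subjects are not replaced, nothing later in the plan restores the number.

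The death wording is a separate inconsistency in the same sentence of Section 20. Read literally, it would class subjects with a primary-endpoint event as not evaluable, which contradicts Section 6 and the Synopsis. It also leaves unclear what the 10% allowance is meant to cover.

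At stake is the accuracy of a stated planning figure that readers will later compare with the number actually analysed.

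**Working it through.** **Inputs.** 404 randomised, 202 per arm (Sections 7 and 14, Synopsis); attrition 10% (Sections 7, 14 and 20); evaluable 368 in total (Section 7) and 184 per arm (Section 20); control rate 49% and test rate 34%, two-sided 0.05, 80% power (Section 14).

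**Step 1: reproduce the plan's total.** 368 × 1.10 = 404.8, close to 404. The added 36 is 36/368 = 9.8% of the evaluable number and 36/404 = 8.9% of the number randomised. This points to an allowance of about 10% taken on the evaluable number.

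**Step 2: apply the stated attrition to the number randomised.**
- Total: 404 × 0.90 = 363.6, against 368. The gap is 4.4 subjects, or 1.2%.
- Per arm: 202 × 0.90 = 181.8, against 184. The gap is 2.2 subjects.
- Number needed to keep 368 after a true 10% loss: 368/0.90 = 408.9, so 409, or 410 with equal arms.
- Largest attrition at which 368 holds: 36/404 = 8.9%.

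**Step 3: effect on power.** The plan names no sample-size formula, so both usual forms are shown. Let Δ = 0.49 − 0.34 = 0.15 and let the mean rate be 0.415. With pooled variance under the null,

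power = Φ[(Δ√n − 1.96·√(2 × 0.415 × 0.585)) / √(0.49 × 0.51 + 0.34 × 0.66)] = Φ[(0.15√n − 1.366) / 0.689].

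For the continuity-corrected version, n is replaced by (n − 1/Δ)²/n. This gives 170.9 for n = 184 and 168.9 for n = 182.

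| Evaluable per arm | Uncorrected | Continuity-corrected |
|---|---|---|
| 184 (as stated) | 83.4% | 80.6% |
| 182 | 83.0% | 80.2% |
| 181.8 (exact) | 83.0% | 80.1% |
| 181 | 82.8% | 79.9% |

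By the same formulas, 80% power needs 169 per arm uncorrected or 182 per arm corrected. About 182 per arm therefore meets the target either way.

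**Step 4: death as attrition.** If deaths count as evaluable, only non-death losses reduce the evaluable number. The full 10% is 40.4 subjects. If 5 of those are deaths, the non-death loss is 35.4 and 404 − 35.4 = 368.6 are evaluable. The documents give no 12-month death rate for this trial. As an illustration only, Section 1 cites mortality of up to 30% at 5 years. At a constant rate that is 1 − 0.70^(1/5) ≈ 7% a year, or at most roughly 28 deaths in 404. So 363.6 applies when the whole 10% is non-death loss.

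**The case against.** The strongest reply is that nothing in the design depends on this. The discrepancy is 1.2%. The primary analysis is intention-to-treat on all enrolled subjects (Section 17), and Section 16 provides missing-data sensitivity analyses and models for censored data. The evaluable count is therefore a rough planning figure. If even 5 of the roughly 40 assumed losses were deaths, at least 368 would be evaluable after all. All of this stands, and it limits the point to a correction of wording. It does not make the two statements correct, because they are worded as floors and Section 20 reaches its floor by counting deaths as losses.

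A reader might infer that the smaller number costs the trial its 80% power. The documents do not support that. Power falls below 80% at 49% versus 34% only if 181.8 is cut to 181 and a continuity correction is applied, and then by about 0.1 point. The plan names no such correction; Section 19 specifies a plain chi-square test. The corrected calculation also gives 364 in total rather than 368, so it is not an exact match for how the plan's figure was obtained.

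A reader might also note that an exact 30% reduction gives 34.3%, where continuity-corrected power is 78.4% at 182 per arm. But it is already 78.9% at the plan's own 184. That shortfall comes from rounding the effect size and from the choice of correction, not from the attrition step.

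**Conclusion.** The point holds as a minor arithmetic and wording error. At the stated maximum of 10% attrition, 404 randomised leave about 364 evaluable (about 182 per arm), which is 4.4 fewer in total than stated. The stated 368 and 184 hold only up to 8.9% attrition. Listing death as attrition in Section 20 contradicts Section 6 and the Synopsis.

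Power at 49% versus 34% falls by about 0.4 of a point and remains at or above 80% under both forms of the calculation. This rests on the plan's event rates, equal arms, a two-proportion comparison on evaluable subjects, and 10% being entirely non-death loss. If part of the 10% is death, the shortfall is smaller or absent. There is no case here for a larger trial.

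**What to change.** Four wording changes:

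1. In Sections 7 and 20, replace the floors of 368 and 184 with about 364 evaluable (about 182 per arm). Alternatively, keep 368 and 184 and state that they assume at most 8.9% attrition.
2. In the Synopsis, make the split of 404 agree with the choice made: 364 + 40 under the first option, or 368 + 36 described as an 8.9% allowance under the second.
3. In Section 20, remove death from the causes of attrition, so that the allowance covers non-death loss only.
4. In Section 14, name the sample-size formula and give the power at the restated evaluable number.

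The cost is editorial. No extra enrolment is needed. The only downside is a slightly less favourable stated evaluable number.
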